5.4.2.2 Disease Control Rate

DCR is defined as the proportion of participants with a best overall response of (1) CR, (2) PR, or (3) stable disease (SD) lasting at least 6 months. Per RECIST, to be assigned a best overall response of CR or PR, changes in tumor measurements must be confirmed by a repeat radiographic assessment performed no less than 4 weeks after the criteria for initial radiographic response were first met. In addition, DCR responders must not have bone lesions that have progressed, as determined by PCWG3 criteria. The duration of SD (or non-CR/non-PD for participants without measurable, soft-tissue disease) is defined as the time from

treatment initiation until the date of radiographic disease progression (per RECIST or PCWG3). If no radiographic progression has occurred and the most recent tumor assessment with overall response of SD occurred within 6 months of treatment initiation, the participant will not have met the SD duration criterion and will not be considered a DCR responder.

Response rates for DCR will be estimated within each cohort and 95% CIs will be estimated using the Clopper-Pearson method.

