1.3 SCHEDULE OF ACTIVITIES

The Schedule of Activities (SOA) shown in [Table 1](#) provides a general overview of the types and timing of the tests and procedures that will be performed in this study. The combination-specific tests and procedures, as well as the timing, will be described in the cohort appendix for each respective combination and will supersede the general overview provided here.

Table 1: Schedule of Activities

Tests & Procedures	Screening/ Enrollment ^a	On-Treatment: Immunotherapy Combination Treatment					End of Treatment ^b	Follow up	
		Cycle 1	Cycle 2	Cycle 3	Cycle 4	Cycle 5 Onward			
Day		To be determined based on immunotherapy combination Refer to the cohort appendix for each respective combination for details on combination-specific timing							14 - 28 days after last dose
Window (days)	-28		± 3	± 3	± 3	± 3	± 7	± 10	± 14
Informed consent ^d	X								
Review of I/E criteria	X								
Medical and cancer history	X								
Physical examination	X	X	X	X	X	X	X		
ECOG performance status	X	X	X	X	X	X	X	X	
Vital signs (see Section 8.2.3)	X	X	X	X	X	X	X		
Body weight ^e	X			X		X (every 3 cycles)	X		
Hematology (see Table 4)	X	X ^f	X ^f	X ^f	X ^f	X ^f	X	X	
Clinical chemistry (see Table 4)	X	X ^f	X ^f	X ^f	X ^f	X ^f	X	X	
Urinalysis	X						X		
Prostate-specific antigen	X	X	X	X	X	X	X	X	
Testosterone level	X								
12-lead ECG ^g	X		X		X				
Circulating tumor cells ^h		X ^f	X ^f	X ^f	X ^f	X ^f	X		
cfDNA (blood) ⁱ	X		X ^f		X ^f		X		
Circulating soluble analytes/PK/ADA ^j	X	X ^f	X ^f	X ^f	X ^f		X		
Blood immune biomarkers ^j	X	X ^f	X ^f	X ^f	X ^f		X		
Archival tumor tissue	X								

Tests & Procedures	Screening/ Enrollment ^a	On-Treatment: Immunotherapy Combination Treatment					End of Treatment ^b	Follow up	
		Cycle 1	Cycle 2	Cycle 3	Cycle 4	Cycle 5 Onward			
Day		To be determined based on immunotherapy combination Refer to the cohort appendix for each respective combination for details on combination-specific timing						14 - 28 days after last dose	110 days after last dose
Window (days)	-28		± 3	± 3	± 3	± 3	± 7	± 10	± 14
Tumor biopsy ^k	X		X				X (at PD [optional]) ^k		
Stool collection ^l	X		X						
Concomitant medications	X	X	X	X	X	X	X	X	
Adverse events	All AEs/AESIs/SAEs will be collected for at least 100 days after the last dose of study intervention ^m								
Immunotherapy combination administration ⁿ		Refer to the cohort appendix for each respective combination for details on study intervention administration							

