Radiographic disease assessment	X	Per PCWG3 guidelines: Every 8 to 9 weeks (± 1 week) for first 24 weeks, and every 12 weeks (± 1 week) thereafter until radiographic PD or start of subsequent therapy. Refer to the cohort appendix for each respective combination for cohort-specific details							
Review of alternate anticancer therapy ^o								X	X
Follow-up for overall survival								X	X

ADA = anti-drug antibodies; AE(s) = adverse event(s); AESI(s) = adverse event(s) of special interest; cfDNA = cell-free deoxyribonucleic acid; ECG = electrocardiogram; ECOG = Eastern Cooperative Oncology Group; EOT = end of treatment; I/E = inclusion/exclusion; PCWG3 = Prostate Cancer Clinical Trials Working Group 3; PD = progressive disease; PD-1 = programmed cell death 1; PK = pharmacokinetics; Q3M = every 3 months; SAE(s) = serious adverse event(s)

^a Tests/procedures performed as standard of care prior to obtaining informed consent and within 28 days prior to the first day of study intervention administration do not have to be repeated at screening.

^b The End of Treatment Visit will be completed following the last dose of study intervention, either at completion of the on-treatment phase or at early discontinuation.

^c For up to 2.5 years from the initiation of study intervention, participants in the follow up phase will be contacted by the site to collect alternate anticancer therapy information and determine survival status.

^d Informed consent must be obtained prior to any study-specific procedures and may be obtained prior to the 28-day screening window.

^e Body weight may be required more frequently for study interventions using weight-based dosing. Combination-specific frequency will be provided in the cohort appendix for each respective combination.

^f Blood samples should be collected prior to administration of any study intervention.

^g 12-Lead ECG will be collected at screening, Cycle 2 and Cycle 4.

^h Circulating tumor cells will be collected at baseline (ie, Day 1 of Cycle 1 prior to study intervention administration), Day 1 of each cycle (prior to study intervention administration), and EOT.

ⁱ cfDNA (blood) will be collected at baseline (ie, screening visit prior to study intervention administration), Day 1 of Cycle 2 and Cycle 4, and EOT.

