8.1 EFFICACY ASSESSMENTS

Participants will undergo tumor assessments as designated in the SOA (see [Section 1.3](#)) regardless of dose delays, until loss of clinical benefit as determined by the Investigator (unless the participant withdraws consent, or the Sponsor terminates the study). All participants who discontinue study intervention for reasons other than disease progression (eg, AEs) will continue tumor assessments for up to 2.5 years from initiation of study intervention or until study completion, death, disease progression, loss to follow-up, withdrawal of consent, or study termination, whichever occurs first. At the Investigator's discretion, tumor assessments may be repeated at any time if PD is suspected.

Measurable and evaluable lesions should be assessed and documented at screening. Tumor assessments performed as standard of care prior to obtaining informed consent and within 28 days prior to the first dose of study intervention do not have to be repeated at screening.

Screening assessments must include computerized tomography (CT) scans (with IV contrast unless contraindicated and oral contrast as appropriate per institutional standards) of the chest, abdomen, and pelvis. A spiral CT scan of the chest may be obtained but is not a requirement. If a CT scan with contrast is contraindicated (ie, in participants with contrast allergy or impaired renal clearance), a non-contrast CT scan of the chest maybe performed and magnetic resonance imaging (MRI) scans of the abdomen and pelvis should be performed. If the participant has a known history of brain metastases or is symptomatic in the opinion of the Investigator, scans of the head should be obtained.

If a CT scan for a tumor assessment is performed in a positron emission tomography (PET)/CT scanner, the CT acquisition must be consistent with the standards for a full contrast diagnostic CT scan.

Bone scans (technetium-99m [TC-99m]) should be performed at screening if clinically indicated. If bone metastases are present at screening and cannot be seen on CT or MRI scans, or if clinically indicated, TC-99m bone scans should be repeated when complete response (CR) is identified in target disease or when progression in bone is suspected.

CT scans of the neck or extremities should also be performed if clinically indicated and repeated throughout the study if there is evidence of disease at screening.

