Appendix Table 1: Response Based on Evaluation of Target Lesions at Each Assessment

Complete response	Disappearance of all target lesions; if a pathologic lymph node, reduction in the shortest axis to < 10 mm ^a
Partial response ^b	$\geq 30\%$ decrease in the sum of the diameters of target lesions relative to the baseline sum diameters ^c
Stable disease ^{b,d}	Neither a sufficient reduction to qualify as a partial response nor a sufficient increase to qualify as progression ^c
Progressive disease ^b	$\geq 20\%$ increase in the sum diameters relative to the smallest sum diameters recorded (including the baseline sum diameters) in conjunction with an increase of at least 5 mm in that smallest sum diameters, or the appearance of 1 or more new lesions ^{c,e}

^a For each pathologic lymph node considered a target lesion, the node must have a short axis measuring < 10 mm to be considered as a complete response. In such cases, the sum diameters may not be zero (as a normal lymph node can have a short axis of < 10 mm).

^b For each pathologic lymph node considered a target lesion, the measurement of the short axis of the node is to be included in the sum diameters when determining partial response, stable disease, and progression.

^c In this study, the “baseline sum diameters” is calculated based on the lesion measurements obtained at screening.

^d Duration of stable disease is measured from the date of the first dose of Study treatment until criteria for progressive disease are met based on the smallest sum diameters recorded (including the baseline sum diameters).

^e The finding of a new lesion should be unequivocal and not possibly attributable to a difference in imaging modality or scanning technique. Post-baseline, fluorodeoxyglucose positron emission tomography (FDG-PET) may be useful in assessing new lesions apparent on CT scan.

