3.4 Analysis Timing

The primary analyses described in the main body of this document will be performed for each immunotherapy combination cohort separately after all participants for a specific cohort have at least 6 months of follow-up from the date of first dose or have discontinued the study. Each cohort will be assessed independently of the other cohorts, and the data from each cohort will be analyzed separately. Study conduct of one or more cohorts may be ongoing at the time of final analysis for a given cohort.

Any cohort-specific modifications to the statistical methods, including any additional cohort-specific endpoints, will be captured as an appendix in this SAP.

Analysis of safety and efficacy endpoints will be performed prior to the time of primary analysis. These analyses will help inform adaptations of the trial, such as expanding, modifying, or terminating a cohort. More information about these interim analyses is presented in Section 5.7. These results may be presented and/or published prior to the primary analysis.

A cohort will formally end once all participants have been followed for survival status for a maximum of 2.5 years or until death, withdrawal of consent, or loss to follow-up. The Sponsor may choose to discontinue survival follow-up of a cohort at any time. A survival analysis of long-term follow-up may be performed after the primary analysis has been completed.

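### If the primary analysis is cut at the permitted 6-month floor, the DCR rule scores recent enrollees in ongoing stable disease as failures, because no scheduled scan on the 8-week grid falls between day 175 and day 245

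*SAP*

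**What the plan says.** - **DCR rule (SAP 5.4.2.2).** A responder has confirmed CR, confirmed PR, or SD of at least 6 months. SD duration runs from treatment start to radiographic progression. For a participant who has not progressed, if "the most recent tumor assessment with overall response of SD occurred within 6 months of treatment initiation, the participant will not have met" the duration criterion. The rule has no scan-window allowance and no category for participants not yet assessable.
- **Protocol convention (Appendix 3, Appendix Table 1, footnote d).** This agrees for progressors: "Duration of stable disease is measured from the date of the first dose of Study treatment until criteria for progressive disease are met".
- **Analysis timing (SAP 3.4).** A cohort's primary analysis is run after all its participants "have at least 6 months of follow-up from the date of first dose or have discontinued the study". The only later analysis named is optional: "A survival analysis of long-term follow-up may be performed after the primary analysis has been completed".
- **Scan schedule (Protocol 1.3, Table 1).** "Every 8 to 9 weeks (± 1 week) for first 24 weeks, and every 12 weeks (± 1 week) thereafter". Cohort appendices "will supersede the general overview provided here"; they are not among the documents reviewed.
- **Denominator (SAP Table 3).** DCR is analysed in the evaluable population. SAP Table 1 instead leaves out participants without measurable disease. The problem is the same under either.
- **Bone lesions (SAP 5.4.2.2).** "DCR responders must not have bone lesions that have progressed, as determined by PCWG3 criteria", with no time limit. The next sentence ends SD duration at progression per RECIST or PCWG3.

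**The concern.** The minimum follow-up equals the SD threshold, but SD beyond that threshold can be shown only by a scan taken after it. On the 8-week grid that scan is due at week 36. At the earliest permitted cut, recent enrollees have not reached it and fail the criterion however they are doing. A participant whose disease progressed in soft tissue at week 36 passes, because the duration is counted to the progression date. What separates the two is length of follow-up, not disease course.

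DCR is a secondary estimate meant to help design later studies. An estimate that depends on accrual speed and cut date serves that purpose poorly, and the exact confidence interval does not reflect the bias.

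The bone wording adds a smaller problem. Two programmers could score bone progression after 6 months differently: one would apply the unlimited bar, the other would count the SD as long enough.

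**Working it through.** The documents give no design figure for DCR to reproduce.

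**Calendar check.** Inputs are the Table 1 schedule on the 8-week reading (weeks 8, 16, 24, 36, each ±7 days from first dose) and 6 months = 6 × 365.25/12 = 182.6 days. The SAP gives no month-to-day conversion; the usual conventions run from 180 to 184 days.

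- Week 24: day 168, window 161 to 175.
- Week 36: day 252, window 245 to 259.

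Under any of these conventions, 6 months lies in the gap from day 175 to day 245.

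**Result needing no accrual assumption.** With the cut 183 days after the last first dose and scans on schedule, a participant first dosed less than 245 − 183 = 62 days before the last one cannot yet have a qualifying SD scan.

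**Two participants compared.** SD at week 24, cut before week 36: last SD scan by day 175, non-responder. SD at week 24, soft-tissue progression on the week-36 scan: duration about 252 days, responder.

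**Size.** Assumptions: n = 15, uniform accrual over A weeks, nominal scan dates, no CR or PR, soft-tissue progression. The floor is 26.1 weeks after the last first dose, so a participant has reached week 36 only if dosed at least 36 − 26.1 = 9.9 weeks before the last.

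Given the last entry time M, the other 14 are uniform on (0, M), and E(1/M) = 15/(14A). Ignoring the negligible chance that M is under 9.9 weeks, the expected number short of week 36, including the last participant, is

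E = 1 + 14 × 9.9 × 15/(14A) = 1 + 148.5/A.

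At full follow-up, DCR under the SAP rule is the proportion progression-free at the week-24 scan. At the cut, the reported DCR is that value × (1 − E/15).

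| Accrual A | E of 15 | 1 − E/15 | 30% becomes | 40% becomes | 50% becomes |
|---|---|---|---|---|---|
| 26 weeks | 6.7 | 0.55 | 17% | 22% | 28% |
| 39 weeks | 4.8 | 0.68 | 20% | 27% | 34% |
| 52 weeks | 3.9 | 0.74 | 22% | 30% | 37% |

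A simulation of 20,000 cohorts per setting, with exponential progression, gave the same values. Moving scans by up to ±1 week changed them by no more than about 0.5 points.

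**Other settings** (accrual 26, 39, 52 weeks; 40% at full follow-up unless stated):

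- Cut at 30 weeks: 28%, 31%, 33%.
- Cut at 34 weeks: 34%, 35%, 36%.
- Cut at 37 weeks: no loss.
- Expanded cohort, n = 30 in two stages of 15: 31%, 34%, 35%.
- 15% confirmed responders, so 15% + 0.85 × 40% = 49%: reported as 34%, 38%, 40%.
- 9-week grid: about 35% to 37% with the third scan at week 27; 31% to 34% with it at week 30.

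**The case against.** **The cut may be later.** Six months is a floor, and the 12-month OS rate in SAP 5.4.2.4 suggests a later cut may be intended. This stands as a limit on size, but nothing in the SAP requires a later cut, and some loss persists until about 37 weeks.

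**The grid is not fixed.** Intervals of 9 weeks are allowed, Table 1 does not say whether windows run from first dose or from the previous scan, and cohort appendices may change the timing. All true. A 9-week grid shrinks the loss at the earliest cut without removing it. If 6 months were programmed as 168 days, scans on days 168 to 175 could qualify; the SAP does not say this.

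**Other scans can fall in the gap.** Protocol 8.1 requires repeat scans 4 to 6 weeks after suspected progression, which after day 168 means days 196 to 210, and allows unscheduled scans when progression is suspected. These do not help participants in unremarkable SD.

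**The benchmark flatters the rule.** Progression-free at week 24 is not the same as controlled at 6 months. Under the exponential model, 40% at week 24 is 0.40^(26.1/24) = 36.9% at 6 months, so against that target the loss is about 3 points smaller. If, as an assumption, 20% of week-24 SD participants stop scans for death, new therapy or loss of benefit, the cut costs 8 to 14 points rather than 10 to 18. Both refinements are fair; neither removes the loss.

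**Sampling error is larger.** For 6 of 15, the exact 95% interval is 16.3% to 67.7% (the interval in SAP Table 2), which covers every value reported for the 40% case. That limits the consequence, but the bias is systematic and avoidable.

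**A later DCR update is not barred.** Correct. None is planned either.

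**Conclusion.** The concern holds. The scan gap and the scoring rule follow directly from the text on the 8-week core grid. At the earliest permitted cut, DCR is biased downward by an amount set by accrual and cut date. Under the stated accrual assumptions, 40% at full follow-up is reported as 22% to 30% in a 15-participant cohort and 31% to 35% in an expanded one.

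These are figures for the earliest cut, and they depend on the assumed accrual and on cohort schedules not seen here. Confirmed CR and PR are unaffected, expansion uses CRR, and the rPFS analysis censors non-progressors instead of failing them. The damage is confined to the DCR table, but the correction is cheap enough that it should be made.

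**What to change.** Keep the 6-month SD definition and add to SAP 3.4 and 5.4.2.2:

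> DCR will be analysed once every participant in the cohort has had the first scheduled tumor assessment later than 6 months after first dose (or its window has closed), or has had radiographic progression, died or discontinued the study.

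If the primary cut cannot move, label DCR at that cut preliminary. Add a sensitivity analysis, labelled a week-24 landmark, that counts SD (or non-CR/non-PD) at the scheduled week-24 scan with no earlier progression as disease control, for later progressors and non-progressors alike.

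In the same edit, reconcile the two bone sentences by stating whether bone progression after 6 months removes responder status.

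**Cost.** SAP wording only. No scans are added: Table 1 already schedules them until radiographic progression or subsequent therapy, and under Protocol 8.1 participants who stop treatment for reasons other than progression "will continue tumor assessments for up to 2.5 years from initiation of study intervention", subject to the listed stopping events. The DCR table is delayed by at most 259 − 183 = 76 days (about 11 weeks) on the 8-week grid. On a 9-week grid the delay is 196 − 183 = 13 days or 217 − 183 = 34 days (about 2 or 5 weeks), with the third scan at week 27 or week 30.

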Appendix Table 3: Evaluation of Overall Response at Each Assessment

Target Lesions	Nontarget Lesions	New Lesions	Overall Response
Complete response	Complete response	No	Complete response
No target lesion ^a	Complete response	No	Complete response
Complete response	Not evaluable ^b	No	Partial response
Complete response	Not complete response/ non-progressive disease	No	Partial response

Target Lesions	Nontarget Lesions	New Lesions	Overall Response
Partial response	Non-progressive disease and not evaluable ^b	No	Partial response
Stable disease	Non-progressive disease and not evaluable ^b	No	Stable disease ^c
Not all evaluated	Non-progressive disease	No	Not evaluable
No target lesion ^a	Not all evaluated	No	Not evaluable
No target lesion ^a	Non-complete response/ non-progressive disease	No	Non-complete response/ non-progressive disease
Progressive disease	Any	Yes or no	Progressive disease
Any	Progressive disease	Yes or no	Progressive disease
Any	Any	Yes	Progressive disease
No target lesion ^a	Unequivocal progressive disease	Yes or No	Progressive disease
No target lesion ^a	Any	Yes	Progressive disease

^a Defined as no target lesions at baseline.

^b Not evaluable is defined as either when no or only a subset of lesion measurements are made at an assessment.

^c The minimum duration on-study required for an overall assessment of stable disease is 49 days.

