5.4.2.3 Radiographic Progression-Free Survival

rPFS is defined as the time from initiation of study intervention to the first objective evidence of radiographic progression or death due to any cause (whichever occurs first). Radiographic disease progression is defined as soft tissue (non-bone) disease progression per RECIST v1.1 or confirmed progression of bone disease per PCWG3 criteria. Participants who continue treatment beyond initial disease progression will be considered to have progression of disease (PD) at the time of the initial progression event.

Participants who do not have radiographic PD at the time of analysis will be censored as follows:

- Participants who do not have radiographic PD and are still on study at the time of analysis will be censored at the date of the last tumor assessment documenting absence of progressive disease
- Participants who have discontinued study treatment and have started subsequent anti-cancer therapy or had subsequent cancer surgery or radiation prior to documentation of radiographic PD will be censored at the date of the last evaluable tumor assessment prior to the initiation of subsequent treatment.
- Participants who discontinued the study prior to documentation of radiographic PD will be censored at the date of the last tumor assessment documenting absence of progressive disease.
- Participants who do not have radiographic PD and who die more than 16 weeks from their last evaluable tumor assessment will be censored at the date of the last tumor assessment documenting absence of progressive disease. Participants who within 16 weeks of their last evaluable tumor assessment will be considered as having an event at the date of death.

rPFS will be estimated using Kaplan-Meier techniques, and the median survival time and 95% CIs will be estimated within each cohort. If median survival is not reached, survival times and 95% CIs will be reported at deciles that are estimable given the observed events.

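### For participants without progression, the six-month DCR test in SAP 5.4.2.2 is tied to the last scan rated SD, so a late unconfirmed response scores as a failure and non-CR/non-PD has no test

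*SAP*

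**What the plan says.** SAP 5.4.2.2 gives three ways to be a DCR responder: a best overall response of CR, of PR, or "stable disease (SD) lasting at least 6 months". CR and PR need a confirming scan at least 4 weeks later. Bone progression by PCWG3 rules a participant out. SD duration is defined as running from "treatment initiation until the date of radiographic disease progression (per RECIST or PCWG3"), and a parenthesis extends this to other participants: "or non-CR/non-PD for participants without measurable, soft-tissue disease". Protocol Appendix Table 1, footnote d, defines SD duration in the same way, from first dose until the criteria for progression are met.

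For a participant with no radiographic progression, the SAP then uses a different anchor. If "the most recent tumor assessment with overall response of SD occurred within 6 months of treatment initiation, the participant will not have met" this 6-month requirement, he is not a DCR responder.

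Three other places bear on this:
- Protocol Appendix Table 3 rates a participant with no target lesion and persistent, non-progressing disease as "Non-complete response/ non-progressive disease". None of its rows for such participants yields SD.
- SAP 5.4.2.3 ties rPFS censoring to any scan without progression: participants are "censored at the date of the last tumor assessment documenting absence of progressive disease".
- SAP Table 1 leaves participants without measurable disease out of DCR. SAP Table 3 analyses DCR on the whole evaluable population, and the parenthesis in 5.4.2.2 also includes them.

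**The concern.** The definition ends SD duration only at progression, so an improved scan does not end it. The clause for participants without progression looks only at scans rated SD and passes over a later scan rated PR or CR. If that later response is unconfirmed, the participant cannot qualify through the CR or PR route, and the SD route measures him from a scan that is no longer his latest. He can be progression-free beyond 6 months and still be counted as uncontrolled.

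The second gap concerns participants rated non-CR/non-PD. They are brought into the duration definition, but the clause for those without progression names a category they never receive. Two programmers could score the same record in opposite ways.

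At stake is the accuracy of a named secondary endpoint that is reported with exact confidence intervals and also used as an outcome in the biomarker associations.

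**Working it through.** The documents state no assumed rate or target for DCR, so there is no plan figure to reproduce. The check applies the rule as written to scan histories.

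**Inputs.**
- Scan schedule, protocol Table 1: every 8 to 9 weeks (± 1 week) for 24 weeks, then every 12 weeks. Cohort appendices may override this. The 8-week grid gives weeks 8, 16, 24, 36 and 48.
- Threshold: 6 months = 365.25/2 = 182.6 days, or 26.1 weeks.
- Scan days: week 24 = 24 × 7 = 168; week 25, the latest in-window date for that scan, = 175; week 36 = 252; week 48 = 336.

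Even a late week-24 scan (day 175) falls before 6 months. On this grid, week 36 is therefore the first scheduled scan that can satisfy the clause.

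**Literal rule against a rule tied to the last scan without progression (PD).** NN = non-CR/non-PD; uPR = unconfirmed PR.

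| | Scan history | As written | Last scan without PD |
|---|---|---|---|
| A | SD 8, 16, 24; uPR 36; no PD | Failure (last SD day 168) | Responder (day 252) |
| B | SD 8, 16, 24, 36; uPR 48; no PD | Responder | Responder |
| C | SD 8, 16, 24; PR 36, confirmed 48 | Responder | Responder |
| D | SD 8, 16, 24; uPR 36; soft-tissue PD 48 | Responder (runs to PD) | Responder |
| E | SD 8, 16; uPR 24; no PD | Failure | Failure |
| F | NN 8, 16, 24, 36; no PD | No rule | Responder |
| G | NN 8, 16; no PD | No rule | Failure |
| H | NN 8, 16, 24; PD 36 | Responder | Responder |
| I | NN 8; PD 16 | Failure | Failure |

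A and D show the contradiction. The same man is a failure while progression-free at day 252 and becomes a responder once soft-tissue disease progresses at day 336. A PR at week 48 would also make him a responder (confirmed), as would SD (last SD scan day 336). His failure at the earlier data cut comes from the anchor, not from his disease.

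On a 9-week grid the scans fall at weeks 9 and 18 and then at week 27 or 30, depending on how the change to 12-week spacing is read. With SD at weeks 9 and 18 and an unconfirmed PR at week 27, the last SD scan is day 18 × 7 = 126 (failure), although the participant is progression-free at day 27 × 7 = 189.

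**Size per participant.** 1/15 = 6.7 points; 1/30 = 3.3 points. As an illustration with assumed counts, reclassifying one participant at n = 15 moves DCR from 3/15 = 20.0% (Clopper-Pearson 4.3% to 48.1%) to 4/15 = 26.7% (7.8% to 55.1%). These two intervals also appear in SAP Table 2 and reproduce exactly.

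**The case against.** The strongest reply is that the affected history is narrow. Failure needs four things together: the last SD scan before 6 months, a later scan after 6 months rated PR or CR, no confirmation, and no progression. Histories B, C and D pass as written, and E fails under either wording. A reader might infer that the test uses only the last SD scan for everyone, or that any unconfirmed PR on the latest scan means failure. The documents support neither, because with progression the duration runs to the progression date.

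A reader might also infer that non-CR/non-PD participants cannot be tested at all. That is too strong: H and I are classified, and only those without progression lack a rule. It is reasonable to carry the parenthesis from the duration sentence into the next one, which would make this part a matter of drafting. If SAP Table 1 governs, these participants are not in DCR and this part falls away.

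Two size arguments are tempting but not established. The minimum of 7 in 15 participants with a biopsiable non-bone lesion does not mean that up to 8 are bone-only or lack measurable disease. Nor must a week-36 PR stay unconfirmed until week 48: a repeat scan 4 weeks later would confirm it, and cohort appendices may set other schedules.

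Finally, DCR is secondary and descriptive, with no type I error control, and expansion uses CRR. All of this limits the size of the problem. It does not remove history A, where a stated rule gives a result opposed to the definition it is meant to apply.

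**Conclusion.** Wrong as written; minor severity. For participants without progression, the clause can score a man as a DCR failure although he is documented progression-free beyond 6 months. This conflicts with the SAP's own definition of SD duration and with protocol Appendix Table 1, footnote d. Read literally, it also leaves non-CR/non-PD participants without progression unclassified, provided they belong in DCR at all, on which the SAP contradicts itself.

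The number affected is probably small and cannot be computed from the documents, which give no rate of late unconfirmed response and no expected share without measurable disease. If 0 to 1 participant per cohort has a late unconfirmed response (an assumption), DCR shifts by 0 to 6.7 points at n = 15, or 0 to 3.3 points at n = 30. The expansion rule is unaffected. The conclusion rests on two readings: that an unconfirmed PR leaves only the SD route open, which follows from the confirmation requirement, and that the general scan schedule applies.

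**What to change.** In SAP 5.4.2.2, for participants without radiographic progression, test the 6 months against the last evaluable tumor assessment that shows no progressive disease, whether it is rated CR, PR, SD or, if those participants are kept in, non-CR/non-PD. This matches the anchor already used for rPFS in 5.4.2.3. It turns history A into a responder, classifies F and G, and leaves the other tabulated histories unchanged.

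In the same edit, reconcile the DCR population. Either SAP Table 1 should include participants without measurable disease, or SAP Table 3 and the parenthesis in 5.4.2.2 should leave them out. Record both changes in SAP Section 6.

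The cost is one phrase and one population statement in the SAP, with the matching lines in the derivation program. No new data are needed.
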